3 INTERIM ANALYSES

Depending on recruitment and data availability, an interim analysis will be performed after the first year, if at least 75% of subjects included have completed one year of follow up.

4 HYPOTHESIS AND ROLE OF DISCUSSION

The statistical significance value is set at $p < 0.05$. The SPSS statistical package version 19.0 or later will be used.

5 ANALYSIS SYSTEMS / POPULATIONS

Considering that 37% of COPD patients will have one moderate/severe exacerbation per year, and assuming that at least 35% of patients will follow their doctor's vaccination

recommendation,³ to have at least 200 vaccinated COPD patients with moderate/severe exacerbations, a total of 1541 eligible subjects should be included in the analysis.

With 35% of patients vaccinated with PCV13, enrolling 1541 eligible subjects with COPD would provide approximately 540 patients in the PCV13 cohort and 1000 patients in the unexposed cohort.

Assuming that 37% of unexposed patients will present one moderate/severe exacerbation per year,² with 70% of the patients remaining in the study after 1 year, this sample size would provide 91% power to detect a statistically significant reduction of 10% in moderate/severe COPD exacerbations with PCV13 after 1 year. Assuming an additional 30% dropout in the second year, the study sample size would provide 91% power to detect a statistically significant reduction of 14% in moderate/severe COPD exacerbations with PCV13 after 2 years.

Time	PCV13		Unexposed		Power	Retention rate
	Sample size	% exacerbation	Sample size	% exacerbation		
Enrollment	540		1000			
1 year	378	27%	700	37%	91.43%	70% from enrollment
2 years	264	60%	490	74%	91%	70% from year 1

5.1 **FULL ANALYSIS**

The statistical analysis of this study will be carried out with all those evaluable patients with COPD, recruited by the Spanish sites participating in the study and who meet the following selection criteria:

5.1.1 **Inclusion Criteria**

Patients must meet all of the following inclusion criteria to be eligible for inclusion in the study:

1. *Aged 18 years or older at the time consent is given*
2. *Patient diagnosed with COPD (any stage, subgroups for analysis will be based on COPD severity)*
3. *Evidence of a personally signed and dated informed consent document indicating that the patient has been informed of all pertinent aspects of the study.*
4. *Ability to understand and complete the required quality of life questionnaires*
5. *Patients with at least 2 years of previous clinical history available relating to (if applicable) history of moderate/severe exacerbations, influenza and pneumococcal vaccination history, comorbidities and previous treatments*
6. *Spirometry data* (maximum 6 months old, or if not available at enrollment, to be performed as per normal clinical practice at visit 1 ± one month)*

*Total proportion of subjects with FEV1 <40 should be less than 20% of the total study population (related to the microbiological etiology dependent on severity)^{14,15}

5.1.2 **Exclusion criteria**

Patients meeting any of the following criteria will not be included in the study:

1. *Impossibility to perform prospective follow up*
2. *Present any immunocompromising condition*
3. *Present any other respiratory disease as a comorbidity (subjects with overlap syndrome COPD-asthma will be excluded. Mixed phenotype defined as: symptoms of increased variability of airflow and incompletely reversible airflow obstruction)³³*

5.2 **SAFETY ANALYSIS**

NA

5.3 **OTHER ANALYSES**

NA

5.4 **SUBGROUPS**

The statistical analyses described in this SAP will be carried out according to the following analysis groups:

Exposed/unexposed (patients vaccinated/not vaccinated with PCV13):

The results will be evaluated through a cohort study, considering the subjects not vaccinated with PCV13 included in the study as the unexposed group.

COPD severity (GOLD):

- GRADE 1: Mild/unknown [$FEV1 \geq 80\%$, $FEV1/FVC < 0.7$ or no spirometry record]
- GRADE 2: Moderate [$50\% \leq FEV1 < 80\%$, $FEV1/FVC < 0.7$]
- GRADE 3: Severe [$30\% \leq FEV1 < 50\%$, $FEV1/FVC < 0.7$]
- GRADE 4: Very severe [$FEV1 < 30\%$ or $FEV1 < 50\%$ plus respiratory failure, $FEV1/FVC < 0.7$])

6 **OBJECTIVES AND VARIABLES**

Given that the primary objective of this study is to evaluate the impact of routine clinical practice vaccination with PCV13 on the reduction of the risk of moderate/severe COPD exacerbations, after 2 years of follow up, and to determine which subgroup of patients (based on the severity of COPD) benefit most from vaccination:

Primary endpoint to be analyzed:

- COPD severity (GOLD)¹⁸
 - GRADE 1: Mild/unknown [$FEV1 \geq 80\%$, $FEV1/FVC < 0.7$ or no spirometry record]
 - GRADE 2: Moderate [$50\% \leq FEV1 < 80\%$, $FEV1/FVC < 0.7$]

- GRADE 3: Severe [$30\% \leq \text{FEV1} < 50\%$, $\text{FEV1/FVC} < 0.7$]
- GRADE 4: Very severe [$\text{FEV1} < 30\%$ or $\text{FEV1} < 50\%$ plus respiratory failure, $\text{FEV1/FVC} < 0.7$])
- Number and severity of exacerbations
- Frequency of total exacerbations (moderate and severe) in previous years and during follow-up.

6.1 **OTHER OBJECTIVES**

For other study objectives, such as to determine the prevalence of PCV13 vaccination in COPD patients or to determine the impact of vaccination on quality of life or the decrease in FEV1:

Secondary endpoints:

- Demographic and epidemiological data;
- Anthropometric data (weight, height, body mass index [BMI], waist circumference)
- Smoking habit, alcohol consumption
- Spirometry data (FEV1, FVC, FEV1/FVC)
- Pharmacological treatment
- Associated comorbidity
 - high blood pressure
 - dyslipidemia
 - type 2 diabetes mellitus
 - metabolic syndrome
 - heart failure
 - ischemic heart disease
 - chronic kidney disease
 - cirrhosis

- History of neoplasia (solid organ and hematologic)
- Pneumococcal vaccination
- Influenza vaccination
- Quality of Life questionnaire (shortened SGRQ, CAT) (completed by the subject and transcribed into the study CRF)

7 **HANDLING OF MISSING VALUES**

In the Saint George Quality of Life scale, ideally there would be no missing values and the questionnaire would be complete; however, if there are missing values, the effect of the missing elements has been examined and the following methods of action are recommended:

Symptoms

The Symptoms component will tolerate a maximum of 2 missed items. The weight for the missed item is subtracted from the total weight for the Symptoms category (662.5) and from the Total weight (3989.4).

Activity

The Activity component will tolerate a maximum of 4 missed items. The weight for the missed item is subtracted from the total weight for the Activity category (1209.1) and from the Total weight (3989.4).

Impacts

The Impacts component will tolerate a maximum of 6 missed items. The weight for the missed item is subtracted from the total weight for the Impacts category (2117.8) and from the Total weight (3989.4).

No criteria for replacement of missing values will be used for the rest of the study variables.

8 **STATISTICAL METHODOLOGY AND STATISTICAL ANALYSIS**

8.1 **STATISTICAL METHODOLOGY**

The results will be evaluated through a cohort study, considering the subjects not vaccinated with PCV13 included in the study as the unexposed group.

- A descriptive analysis of all variables will be performed. Qualitative variables will be analyzed by absolute and relative frequencies. Quantitative variables will be studied using the usual measures of central tendency and dispersion (mean, median, standard deviation, confidence intervals, minimum, maximum and interquartile range).

- For comparison of independent samples, the Pearson's Chi-squared test or the Fisher's exact test for 2x2 tables or likelihood ratio for mXn tables will be used for qualitative variables. The Student's t-test, one-way ANOVA or its non-parametric equivalents, the Mann-Mann U test or Kruskal-Wallis H test, will be used for quantitative variables.
- For comparison of paired samples, the McNemar's test will be used for qualitative variables and the Student's t-test or Wilcoxon's test for quantitative variables.
- The study will seek to identify factors associated with the occurrence of exacerbations throughout the follow-up period; to that end, a multivariate logistic regression analysis will be performed, where the dependent variable will be the occurrence of exacerbations (Yes/No) during the study. Vaccination with PCV13 and significant variables in the univariate model will be used as possible risk factors: demographic characteristics, influenza vaccination, smoking habit, etc. In addition, potential confounding variables will be considered: exacerbator phenotype, comorbidities, COPD severity, FEV1 (no control possible based on the study design).
- Appropriate tests will be performed accordingly to determine if the necessary requirements are fulfilled for the use of parametric tests.
- Estimates will be performed with a 95% confidence interval. The SPSS statistical package, version 19.0 or later, will be used.

8.2 **STATISTICAL ANALYSIS**

8.2.1 **Patient disposition**

The absolute and relative frequency of evaluable patients will be determined. In the subpopulation of non-evaluable patients, the frequency distribution will be presented based on the reasons for non-evaluation:

- Patient under 18 years of age at the time of obtaining informed consent
- Not diagnosed with COPD of any grade (patients diagnosed with COPD less than 2 years after inclusion in the study should not be included)
- At least two years of prior medical records are not available relating to (if applicable):
 - History of moderate/severe exacerbations
 - History of influenza vaccination (date)
 - History of pneumococcal vaccination (date)
 - Comorbidities
 - Previous treatments
- No spirometry data available
- Inability to understand and complete the required quality of life questionnaires
- No evidence of a personally signed and dated informed consent document indicating that the subject has been informed of all pertinent aspects of the study
- Impossibility to perform prospective follow-up
- Present any immunocompromising condition

- Present any other respiratory disease as comorbidity

In the subpopulation of evaluable patients, the frequency distribution will be given according to the analysis groups:

Exposed/unexposed patient:

- Patient with COPD of any grade vaccinated with PCV13
- Patient with COPD of any grade not vaccinated with PCV13

In the subpopulation of exposed patients and provided that we have a sufficient frequency, a new analysis group will be established based on:

- **PCV13 only**
- **PCV13+ PPV23**
- **PCV13+ Influenza (same summer period)**
- **PCV13+ PPV23+influenza (same summer period)**

COPD severity:

- GRADE 1: Mild/unknown [$FEV1 \geq 80\%$, $FEV1/FVC < 0.7$ or no spirometry record]
- GRADE 2: Moderate [$50\% \leq FEV1 < 80\%$, $FEV1/FVC < 0.7$]
- GRADE 3: Severe [$30\% \leq FEV1 < 50\%$, $FEV1/FVC < 0.7$]
- GRADE 4: Very severe [$FEV1 < 30\%$ or $FEV1 < 50\%$ plus respiratory failure, $FEV1/FVC < 0.7$])

The statistical analysis detailed below will be performed both with the total sample of evaluable patients and divided based on the two analysis groups established: exposed/unexposed and severity of COPD.

Additionally, a flow chart will be presented on the total number of patients analyzed at each of the study follow-up visits:

- Month 1
- Month 6
- Month 12
- Month 18
- Month 24

In the subpopulation of ineligible patients at each of the scheduled visits, the frequency distribution will be given based on the reason for ineligibility:

- Does not meet one or more of the inclusion criteria:
 - a) Aged ≥ 18 years at the time of obtaining informed consent
 - b) Diagnosed with COPD of any grade
 - c) With at least 2 years of previous clinical history available relating to (if applicable): history of moderate/severe exacerbations, history of influenza vaccination (date), history of pneumococcal vaccination (date), comorbidities and previous treatment
 - d) Spirometry data (if available at enrollment, should be a maximum of 6 months old. If not available at enrollment, perform as per routine clinical practice at visit 1 ± 1 month.
 - e) Ability to understand and complete the required quality of life questionnaires
 - f) Existence of a personally signed and dated informed consent document indicating that the subject has been informed of all pertinent aspects of the study
- Meets one or more of the inclusion criteria:
 - g) Impossibility to perform prospective follow-up
 - a. Death
 - b. Moved to another region
 - c. Other reason
 - h) Present any immunocompromising condition
 - i) Present any other respiratory disease as a comorbidity (subjects with asthma-COPD overlap syndrome will be excluded)

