#### **8.5. Study size**

With 35% patients vaccinated with PCV13, enrolling 1540 eligible COPD patients will provide approximate 540 patients in PCV13 cohort and 1000 patients in the control cohort.

Assuming 37% of the control patients experiencing moderate/severe exacerbation per year with 70% of the patients remaining in the study at year 1, this sample size will provide 91% power to detect a statistical significant reduction of 10% on COPD moderate/severe exacerbations from PCV13 after 1-year. Assuming additional 30% dropout from year 2, the study sample size will provide 91% power to detect a statistical significant reduction of 14% on COPD moderate/severe exacerbations from PCV13 after 2-year.

Time	PCV13		Control		Power	Retention Rate
	Sample Size	% exacerbation	Sample Size	% exacerbation		
Enrollment	540		1000			
1-year	378	27%	700	37%	91.43%	70% from Enrollment
2-Year	264	60%	490	74%	91%	70% from Year 1

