## **8.7. Data analysis**

Depending on recruitment and data availability an interim analysis may be performed after the first year, if at least 75% of subjects included have completed one year of follow up.

- To determine the impact of PCV13 vaccination, the incidence of exacerbations will be determined 2 years after the inclusion in the study and will be compared with the incidence 2 years before the study (2 years of clinical history required including records of previous moderate/severe exacerbations, influenza and pneumococcal vaccination history comorbidities and previous treatments)
- A descriptive analysis of all variables will be performed. Qualitative variables will be analyzed by absolute and relative frequencies. Quantitative variables will be studied by the usual centralization and dispersion measures (mean, median, standard deviation, confidence intervals, minimum, maximum and interquartile range).
- For comparison of independent samples, the Pearson chi-squared test or the exact Fisher test for 2x2 tables or likelihood ratio for mXn tables, for qualitative variables, will be used. The Student's t test, one-way ANOVA or its non-parametric equivalent U-Mann-Mann, H-Kruskal-Wallis for quantitative variables will be used.
- For comparison of paired samples, the McNemar's test will be used for qualitative variables and Student's t test or Wilcoxon's test for quantitative variables.
- A multivariate logistic regression analysis will be performed, in order to identify risk factors associated with exacerbations. Exacerbations existence (yes/no) will be used as dependent variable. Vaccination with PCV13 and statistically significant variables in the univariate model, will be used as possible risk factors: demographic characteristics, influenza vaccination, smoking habit, etc. In addition, potential confounding variables will be considered: phenotype, comorbidities, COPD severity, FEV1 (no control possible based on the study design)
- Appropriate tests will be performed accordingly to determine if the necessary requirements are fulfilled for the use of parametric contrasts.
- Estimates will be performed with a 95% confidence interval. The SPSS statistical package version 19.0 or later will be used.

Redacted

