The aim of this study is to generate evidence to support vaccination of COPD patients with PCV13 and/or against influenza in terms of clinical benefits and quality of life.

2.1 **STUDY DESIGN**

Prospective observational study, which will be carried out in 6 different geographical areas in Spain (Salamanca, Cantabria, Palma de Mallorca, Madrid, Barcelona and Seville), involving 1 hospital in each region.

Subjects identified with COPD will be invited to participate by investigators at the time of their routine follow-up visits. All therapies will be prescribed in line with routine clinical practice according to the updated National COPD Guidelines (GesEPOC),¹ indicating among other therapies active reduction of risk factors, and influenza and pneumococcal vaccination (with PCV13) in all patients with mild, moderate or severe COPD. All patients will be advised to quit smoking and recommended healthy lifestyle habits.

Study will include periodic visits for all patients, to complete a total follow up of 2 years.

2.2 **STUDY OBJECTIVES**

The study objectives are to:

- **Primary objectives**

1. Evaluate the impact of routine clinical practice vaccination with PCV13 on the reduction of the risk of moderate/severe COPD exacerbations, after 2 years of follow-up.
2. Determine which subgroup of patients (based on the severity of COPD) benefit most from vaccination with PCV13

COPD severity (GOLD)¹⁸

- GRADE 1: Mild/unknown [$FEV1 \geq 80\%$, $FEV1/FVC < 0.7$ or no spirometry record]
- GRADE 2: Moderate [$50\% \leq FEV1 < 80\%$, $FEV1/FVC < 0.7$]
- GRADE 3: Severe [$30\% \leq FEV1 < 50\%$, $FEV1/FVC < 0.7$]
- GRADE 4: Very severe [$FEV1 < 30\%$ or $FEV1 < 50\%$ plus respiratory failure, $FEV1/FVC < 0.7$])

- **Secondary objectives**

1. Evaluate the impact of influenza and PCV13 vaccination on the reduction of the risk of exacerbations
2. Evaluate the impact of vaccination with PCV13 on patients' quality of life
3. Evaluate the impact of vaccination with PCV13 on the decrease in FEV1
4. Estimate the potential savings for the healthcare system derived from vaccination of COPD patients with PCV13
5. Determine the prevalence of PCV13 vaccination in COPD patients.

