8.2.3 Effectiveness analysis

8.2.3.1 Study of exacerbations

A detailed analysis of the total number of exacerbations reported by the study patients will initially be performed. The absolute and relative frequency of patients who have reported at least two moderate exacerbations or one severe exacerbation per year (exacerbator patient) will be given.

The following indices will be calculated:

- NEPA (number of exacerbations patient/year) = Total no. of exacerbations reported by patients/ Patient follow-up time^{*)}
- NEPA Mild = Total no. of mild exacerbations/Patient follow-up time
- NEPA Moderate = Total no. of moderate exacerbations/Patient follow-up time
- NEPA Severe = Total no. of severe exacerbations/Patient follow-up time
- NEPA Moderate/severe = Total no. of moderate_severe exacerbations/Patient follow-up time

The following will also be calculated in the subpopulation of exposed patients:

- NEPA_pre_PCV13 = Total no. of exacerbations reported by the patient prior to receiving the PCV13 / Time to vaccination with PCV13^{**)}
- NEPA_pre_PCV13 (moderate/severe) = Total no. of moderate/severe exacerbations reported by the patient prior to receiving the PCV13 / Time to vaccination with PCV13^{**)*)}
- NEPA_post_PCV13 = Total no. of exacerbations reported by the patient after receiving the PCV13 / Time since vaccination with PCV13^{***)}
- NEPA_post_PCV13 (moderate/severe) = Total no. of moderate/severe exacerbations reported by the patient prior to receiving the PCV13 / Time since vaccination with PCV13^{***)}

*) Time from the date of COPD diagnosis to the date of the last follow-up visit. If the date of diagnosis of the disease is unknown, it will be computed as two years before the date of inclusion of the patient in the study

**) Time from date of COPD diagnosis to date of PCV13 vaccination

***) Time from vaccination with PCV13 to date of the last follow-up

Each of the indices calculated above will be described using the main measures of central tendency and dispersion (mean, median, standard deviation, confidence intervals, minimum, maximum and interquartile range).

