The Student's t test, one-way ANOVA or its non-parametric equivalents, the Mann-Mann U test or Kruskal-Wallis H test will be used to determine if statistically significant differences are observed in NEPA, NEPA Mild, NEPA Moderate, NEPA Severe and NEPA Moderate/Severe according to the severity of COPD and type of patient (exposed/unexposed). In order to determine the impact of PCV13 vaccination on exacerbations, paired data comparisons will be made between (NEPA_pre_PCV13 vs. NEPA_post_PCV13) and (NEPA_pre_PCV13 (moderate/severe) vs. NEPA_post_PCV13 (moderate/severe)), using the Student's t-test for paired data or its non-parametric equivalent, the Wilcoxon test.

In order to study which subgroups of patients obtain a greater benefit from vaccination

with PCV13 according to COPD severity, paired data comparisons will be made between (NEPA_pre_PCV13 vs. NEPA_post_PCV13) and (NEPA_pre_PCV13 (moderate/severe) vs. NEPA_post_PCV13 (moderate/severe)), in each of the four patient subpopulations established based on disease severity.

In order to determine the factors associated with the presence of an exacerbator patient, a logistic regression model will be constructed, whose dependent variable is (exacerbator/non-exacerbator patient) and, as independent variables, all those possible factors that have been significant in the univariate models ($p_{value} < 0.25$), following the methodology of Hosmer-Lemeshow.

- ❖ Vaccine exposure (PCV13 yes/no)
- ❖ COPD severity (Grade I, Grade II, Grade III, Grade IV)
- ❖ Age
- ❖ Sex
- ❖ Time since diagnosis of the disease
- ❖ Patient with stable treatment for at least three months
- ❖

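### The objective and sample size are on the risk scale, but both covariate-adjusted PCV13 comparisons are logistic models and no adjusted risk difference or risk ratio is planned

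*SAP*

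**What the plan says.** The first primary objective (SAP 2.2; Protocol 7) concerns the "reduction of the risk of moderate/severe COPD exacerbations, after 2 years of follow-up". The sample size (Protocol 8.5; SAP 5) is built on the proportion of patients with a moderate/severe exacerbation. At 1 year this is 27% with PCV13 against 37% without; at 2 years it is 60% against 74%. Protocol 8.5 describes the 2-year target as a "reduction of 14% on COPD moderate/severe exacerbations from PCV13 after 2-year", which the table shows to be an absolute difference.

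Two planned exacerbation analyses carry covariates:

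- SAP 8.1: "a multivariate logistic regression analysis will be performed, where the dependent variable will be the occurrence of exacerbations (Yes/No) during the study". Protocol 8.7 has the same model: "Exacerbations existence (yes/no) will be used as dependent variable". On covariates, SAP 8.1 says: "Vaccination with PCV13 and significant variables in the univariate model will be used as possible risk factors".
- SAP 8.2.3.1: a logistic model for exacerbator status, an exacerbator being a patient with "at least two moderate exacerbations or one severe exacerbation per year (exacerbator patient". PCV13 exposure is one of the candidate factors screened at a univariate p-value below 0.25.

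The remaining exacerbation comparisons in SAP 8.2.3.1 are unadjusted. They are t, ANOVA or rank tests on the exacerbation rate per patient-year (NEPA) by exposure group and by GOLD grade, and paired before/after tests within vaccinated patients. SAP 8.1 promises 95% confidence intervals but names no effect measure for the logistic models.

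**The concern.** Vaccination follows routine practice. The unvaccinated group includes patients who were not offered the vaccine, did not take it up, or had a contraindication (Protocol 8.1). Crude group comparisons are therefore open to confounding, and an adjusted between-group estimate is needed to answer the primary objective. The only adjusted effect the plan produces is a logistic coefficient, which exponentiates to an odds ratio.

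When most patients have the event, the odds ratio is much further from 1 than the risk ratio. The adjusted result then cannot be compared with the 10-point and 14-point differences the study was sized to detect, and it does not express a reduction of risk in the sense of the objective.

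**Working it through.** **Inputs** (Protocol 8.5 and SAP 5, same table): 1 year, 27% of 378 v 37% of 700; 2 years, 60% of 264 v 74% of 490. Significance level 0.05 (SAP 4), taken as two-sided because no side is stated.

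**The plan's own power figures.** Two proportions, pooled variance under the null: power = Φ[(|p1 − p2| − 1.96·SE0)/SE1].

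- 1 year: pooled proportion 361.06/1078 = 0.335, SE0 = 0.0301, SE1 = 0.0292; (0.10 − 0.0590)/0.0292 = 1.40, power 91.9%. The plan states 91.43%, so this row reproduces.
- 2 years: pooled proportion 521/754 = 0.691, SE0 = 0.0353, SE1 = 0.0361; (0.14 − 0.0691)/0.0361 = 1.96, power 97.5%. The plan states 91%, which this calculation does not reproduce. That is a separate matter and does not enter the effect measures below.

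The 1-year reproduction supports reading the targets as absolute differences between proportions.

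**Effect measures on the plan's rates.** OR = [p1/(1 − p1)]/[p2/(1 − p2)]; RR = p1/p2; RD = p1 − p2.

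- 2 years: OR = (0.60/0.40)/(0.74/0.26) = 0.527, 47.3% lower odds. RR = 0.60/0.74 = 0.811, 18.9% lower risk. RD = −14 points. Ratio of the two relative reductions: 47.3/18.9 = 2.5.
- 1 year: OR = (0.27/0.73)/(0.37/0.63) = 0.630, 37.0% lower odds. RR = 0.27/0.37 = 0.730, 27.0% lower risk. RD = −10 points. Ratio: 37.0/27.0 = 1.4. SAP 8.1 models occurrence during the study, so this row bears only on the conditional interim analysis (SAP 3).

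**Sensitivity to the 2-year row.** The 74% is 2 × 37%, while 2 × 27% would be 54%, not the 60% used. If the annual risks are instead compounded over two independent years (an assumption):

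- Unvaccinated: 1 − 0.63² = 60.3%. Vaccinated: 1 − 0.73² = 46.7%.
- OR = (0.4671/0.5329)/(0.6031/0.3969) = 0.577, 42.3% lower odds. RR = 0.4671/0.6031 = 0.774, 22.6% lower risk. RD = −13.6 points. Ratio: 42.3/22.6 = 1.9.

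**Effect of adjustment itself.** The figures above are crude odds ratios. As an illustration, take a normally distributed covariate independent of vaccination and keep the marginal risks at 60% and 74%. The covariate-conditional odds ratio is 0.51, 0.47 or 0.41 when the covariate's standard deviation on the logit scale is 0.5, 1 or 1.5 (assumed values). The odds ratio moves away from 1 with no confounding present, while the marginal risk difference stays at 14 points.

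**The case against.** Four points stand on the other side.

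- A reader might infer that the plan will present a 47% reduction in risk, or that the logistic model is wrong. The documents support neither. Neither one mentions an odds ratio. SAP 8.1 gives the model's purpose as finding factors associated with exacerbations, and SAP 8.2.3.1 assigns the impact of vaccination to paired before/after NEPA tests in vaccinated patients. An odds ratio labelled as such is a correct summary. Overstatement of benefit is a risk in interpretation, not a planned step.
- A reader might also carry 47% v 19% over to both logistic models. The exacerbator outcome in SAP 8.2.3.1 has no planned frequency, so no such figure can be given. That model may not even retain a PCV13 term.
- Group proportions should be available. SAP 8.1 plans frequencies and chi-squared or Fisher comparisons for qualitative variables, and SAP 8.2.1 splits results by exposure. A crude risk difference can therefore be set beside the targets. Only the adjusted one is missing.
- A risk-scale summary inherits the model's weaknesses. SAP 8.1 says "potential confounding variables will be considered: exacerbator phenotype, comorbidities, COPD severity, FEV1 (no control possible based on the study design", which leaves the extent of adjustment unclear, and covariates are chosen by univariate significance.

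These points limit the claim but do not remove it. The impact analysis that the SAP does name is unadjusted and has no unvaccinated comparator. The objective therefore still lacks an adjusted between-group estimate on its own scale.

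**Conclusion.** The gap is real and is one of reporting scale, so it is a cheap improvement and not an error in the logistic model. At 2 years the relative reduction looks about 1.9 to 2.5 times larger as odds than as risk: 42% v 23% on compounded annual rates, 47% v 19% on the plan's table.

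This rests on three assumptions:

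- The planning rates, which are for moderate/severe events, carry over to the SAP 8.1 outcome. That outcome is not restricted by severity; if mild events count, it is at least as common.
- The 19% is derived as 1 − 60/74. The plan itself states 14%, which is absolute.
- The lower end of the range treats the two years as independent.

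**What to change.** In SAP 8.1:

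1. State that PCV13 stays in the model whatever its univariate result.
2. Define the outcome as at least one moderate/severe exacerbation during follow-up, to match the objective and the sample size.
3. Beside the odds ratio, report an adjusted risk difference and risk ratio with 95% CI. Standardise the fitted logistic model: predict each patient's risk with PCV13 set to yes and then to no, average each over the whole cohort, take the difference and the ratio, and bootstrap the interval. Poisson regression with robust variance is an alternative for the risk ratio only.
4. State that risk reduction in the report means these measures, and label the odds ratio as a change in odds.

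The cost is SAP wording and a little extra analysis, with no new data. The sponsor should check whether item 2 counts as a major modification needing a protocol amendment under the rule at the end of Protocol 8.7. The reported figure will look less dramatic. The change does not cure residual confounding, univariate covariate selection or the planned 30% loss in each year.

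### The adjusted Yes/No exacerbation model has no time window or follow-up term and no rule for patients who leave early, although the plan expects to lose 51% by two years

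*SAP*

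**What the plan says.** SAP 8.1 plans a multivariable logistic regression in which "the dependent variable will be the occurrence of exacerbations (Yes/No) during the study". Protocol 8.7 agrees: "Exacerbations existence (yes/no) will be used as dependent variable". On covariates the SAP says "Vaccination with PCV13 and significant variables in the univariate model will be used as possible risk factors". Follow-up time is not among the factors named, and no offset or fixed observation window is given.

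The sample-size text in SAP 5 (and Protocol 8.5) starts from "approximately 540 patients in the PCV13 cohort and 1000 patients in the unexposed cohort". It continues "with 70% of the patients remaining in the study after 1 year", and for the two-year figure "Assuming an additional 30% dropout in the second year". The same retention is applied to both cohorts.

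On missing data, SAP 7 gives an item rule for the St George questionnaire and then states "No criteria for replacement of missing values will be used for the rest of the study variables". SAP 5.1 analyses all evaluable patients and does not make 24 months of follow-up a condition. Protocol 8.9 admits that loss to follow-up may bias the results but offers no remedy.

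SAP 8.2.3.1 uses person-time for the exacerbation rates (NEPA). These are compared between exposed and unexposed patients without covariates, and their time runs from COPD diagnosis. The same section has a second logistic model, for exacerbator status, also without a follow-up term.

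**The concern.** A Yes/No outcome over whatever time each patient happened to be observed is not one quantity. A patient lost at month 3 without an event and a patient followed event-free for 24 months would carry the same value if both are scored No. With about half the cohort expected to leave, the handling of early leavers could decide the result, and the plan leaves it open. Two analysts could follow the SAP faithfully and report different odds ratios for PCV13.

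This matters because vaccination is not randomised, so the comparison depends on adjustment, and adjustment occurs only in the two logistic models. The analyses that account for time do not adjust, and the analyses that adjust do not account for time.

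**Working it through.** **1. The plan's own retention figure.** 540 × 0.7 × 0.7 = 264.6 (tabulated as 264) and 1000 × 0.7 × 0.7 = 490. Together 264 + 490 = 754 of 1540, or 49% retained and 51% lost. This reproduces.

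**2. Inputs.** SAP 5 states: "Assuming that 37% of unexposed patients will present one moderate/severe exacerbation per year". The PCV13 figure at one year is 27%. The two-year row gives 60% versus 74%. Assumptions of this check: constant event rate λ, constant dropout rate δ independent of events, and early leavers without an event scored No. Then

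P(Yes) = λ/(λ+δ) × [1 − exp(−2(λ+δ))].

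The 37% refers to moderate/severe exacerbations, whereas the SAP 8.1 outcome has no severity limit, so the results show the mechanism rather than predict the estimate.

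**3. Equal retention, as the documents assume.**
- Control: λ = −ln 0.63 = 0.462 and δ = −ln 0.70 = 0.357. The full two-year risk is 1 − 0.63² = 60.3%. P(Yes) = 0.564 × 0.805 = 45.5%.
- PCV13: the rate ratio is ln 0.73 / ln 0.63 = 0.68, so λ = 0.314. The full risk is 46.7% and P(Yes) is 34.6%.
- Full-follow-up odds ratio: (0.467/0.533)/(0.603/0.397) = 0.58. As scored: (0.346/0.654)/(0.455/0.545) = 0.63.
- With the plan's two-year risks, λ = −ln(0.40)/2 = 0.458 and −ln(0.26)/2 = 0.674. P(Yes) is 45.2% versus 57.0%. The odds ratio moves from 0.53 to 0.62.
- With no vaccine effect it stays at 1.00.

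**4. Unequal retention (assumed), no vaccine effect.**
- At 37% per year, yearly retention of 75% with PCV13 and 65% without gives 47.9% versus 43.1%, an odds ratio of 1.21. The reverse gives 0.82.
- At the 74% two-year risk, 75% versus 67% keeps overall retention at about 49% and gives 1.20. An unadjusted two-sided 5% test on 540 versus 1000 would then reject a true null about 39% of the time.

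**5. Unequal follow-up with equal dropout.** Protocol 8.2 allows vaccination before or after inclusion. A patient who leaves before being vaccinated remains unexposed, so patients classed as ever vaccinated are observed longer. Simulation with no vaccine effect, 37% events per year and 70% yearly retention for everyone, assuming 35% intended uptake and late vaccinations spread evenly over year 1, gives:

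| Share vaccinated after inclusion (assumed) | Null odds ratio, ever versus never vaccinated | Null odds ratio, event before vaccination classed as unexposed |
|---|---|---|
| 25% | about 1.09 | about 0.95 |
| 50% | about 1.18 | about 0.89 |
| 100% | about 1.42 | about 0.76 |

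The direction turns on an exposure-coding choice that the SAP does not make for this model.

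**6. The alternatives.** If early leavers are excluded, 1540 − 754 = 786 patients drop out of the analysis. Under independent dropout, completers recover the odds ratio (0.53, or 1.00 under the null), and a person-time analysis recovers the rate ratio (0.68, or 1.00), in every retention scenario simulated at the plan's 60% versus 74%. The completers result fails if dropout depends on the risk of exacerbation.

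**The case against.** A reader might infer that dropouts will be counted as No. The documents do not say so, and some passages lean towards exclusion: SAP 8.2.1 lists impossible follow-up as a reason for non-evaluability and places patients who died or moved in an ineligible group at each visit, and the power table uses retained numbers. This stands. The figures in steps 3 to 5 hold only under the No coding, and nothing in the plan settles the choice.

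A reader might also infer that this is the only adjusted analysis. It is not, since SAP 8.2.3.1 has the exacerbator model. That outcome is defined per year, but the model is still binary with no follow-up term.

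The SAP presents the 8.1 model as a search for associated factors and assigns the impact of PCV13 to paired pre/post NEPA comparisons. This limits the consequence, because the primary conclusion does not rest on this model alone. It does not supply an adjusted estimate that respects follow-up time.

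The documents assume equal retention in both cohorts, so a claim that the odds ratio will be biased without any vaccine effect goes beyond them. This stands for dropout alone. Late vaccination can still make follow-up unequal, to an unknown extent.

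Finally, missed visits need not mean lost outcomes. Protocol 8.2 and 8.4 give access to hospital and primary care records, and 9.2 asks for outcomes to be documented after withdrawal. This could shrink the problem, but the SAP does not say that exacerbation status will be completed from records to month 24.

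**Conclusion.** The concern holds as an under-specification with a clear better method available. The adjusted model has no window, follow-up term or coding rule for early leavers, against 51% expected loss, and no adjusted analysis in the SAP uses person-time.

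If early leavers without an event are scored No, equal retention attenuates the odds ratio (0.58 to 0.63, or 0.53 to 0.62) and does not create an effect. A null odds ratio moves only with unequal follow-up: to 1.21 or 0.82 for a 10-point gap in yearly retention, and to about 1.09 to 1.42 from late vaccination on the ever-vaccinated coding. The retention gaps and the late-vaccination share are assumptions with no source in the documents. All these figures also assume constant rates and independent dropout. If early leavers are excluded, the cost is about half the cohort and reliance on non-informative dropout.

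**What to change.** Replace the Yes/No logistic model with an adjusted Cox model for time to first moderate/severe exacerbation after inclusion. Enter PCV13 as a time-dependent covariate using the protocol's 15-day rule, and censor at last contact. An adjusted count model, or a complementary log-log model, with log follow-up time since inclusion as offset is an acceptable alternative. In either case:

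- define last contact, and say whether medical records extend it beyond the last attended visit;
- tabulate timing and reasons of loss by exposure group, which extends the visit flow chart and ineligibility reasons already planned;
- add a sensitivity analysis for informative dropout.

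The protocol already defines exacerbation onset dates, and SAP 8.2.1 refers to dates for pneumococcal vaccination history, so the main data needs appear to be met; vaccination dates during follow-up should be confirmed in the case report form. The cost is a SAP revision and some extra analysis work. Protocol 8.7 requires a protocol amendment if the sponsor regards this as a major change to the primary analysis.
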